10.5 Assessment of Performance

The secondary endpoints of this study (operative time, device-related conversions, device deficiencies) will assess the overall performance of the Medtronic Hugo™ RAS System when used for urologic robotic surgery. Secondary endpoints will evaluate the safety and performance of the study device and will not evaluate specific label claims.

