Relatedness	
System Related (Includes all components of the Hugo™ RAS System, associated introduction tools, operational and installed software and programmers as defined in the CIP)	An AE that results from the presence or performance of any component of the system. Device-related: An AE that results from the presence or performance (intended or otherwise) of the device. Refer to Section 7.1 . Investigational Feature: An AE that results from the presence or performance (intended or otherwise) of the Hugo™ RAS System.
Procedure Relatedness	An AE that occurs due to any procedure related to the Hugo™ RAS System.
Underlying Condition or Disease Relatedness	Underlying condition refers to a chronic disease or condition that a subject has prior to any acute treatment/surgery (like diabetes, heart disease, obesity, cancer, etc.).
Relatedness Classification (Procedure, underlying condition, or device)	Not related: relationship can be excluded when: 
the event has no temporal relationship with the use of the device or procedure;the event does not follow a known response pattern to the device (if the response pattern is previously known) and is biologically implausible;the discontinuation of device application or the reduction of the level of activation/exposure - when clinically feasible – and reintroduction of its use (or increase of the level of activation/exposure), do not impact on the event;

Medtronic Business Restricted

This document is electronically controlled

CONFIDENTIAL 056-F275 Rev E Clinical Investigation Plan Template

Medtronic Expand URO Clinical Investigation Plan

- the event involves a body-site or an organ not expected to be affected by the device or procedure;
- the event can be attributed to another cause (e.g., an underlying or concurrent illness/ clinical condition, an effect of another device, drug, treatment or other risk factors);
- the event does not depend on a false result given by the device used for diagnosis, when applicable;

In order to establish the non-relatedness, not all the criteria listed above might be met at the same time, depending on the type of device/procedures and the event.

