	Cystectomy	500 mL	The mean effect size is 133.0 with a 95% confidence interval of 102.6 to 163.4. The 95% prediction interval was not able to be obtained due to a lack of data. As there are few literature cohorts available for this endpoint, the performance goals of the other two surgical cohorts were considered in setting this endpoint's performance goal of 500.
Transfusion rate	Nephrectomy	30%	The mean effect size is 0.079 with a 95% confidence interval of 0.056 to 0.11. The 95% prediction interval is 0.021 to 0.257. A performance goal of 0.30 is clinically appropriate for descriptive comparison.
	Prostatectomy	60%	The mean effect size is 0.020 with a 95% confidence interval of 0.011 to 0.037. The 95% prediction interval is 0 to 0.534. A performance goal of 0.60 is clinically appropriate for descriptive comparison.
	Cystectomy	55%	The mean effect size is 0.133 with a 95% confidence interval of 0.050 to 0.308. The 95% prediction interval is 0.004 to 0.869. While below the 95% prediction interval upper limit, a performance goal of 0.550 is better aligned for a descriptive comparison.
Rate of device-related conversion	Nephrectomy	15%	The literature search failed to identify studies that reported on device-related conversions. Device related conversions are expected to be a fraction of the total conversions. Conversion Rate = 100% - Surgical Success Rate, which has a performance goal of 85%. Thus, a 15% performance goal is assumed for conversions.
	Prostatectomy	15%	The literature search failed to identify studies that reported on device-related conversions. Device related conversions are expected to be a fraction of the total conversions. Conversion Rate = 100% - Surgical Success Rate, which has a performance goal of 85%. Thus, a 15% performance goal is assumed for conversions.
	Cystectomy	15%	The literature search failed to identify studies that reported on device-related conversions. Device related conversions are expected to be a fraction of the total conversions. Conversion Rate = 100% - Surgical Success Rate, which has a performance goal of 85%. Thus, a 15% performance goal is assumed for conversions.

Medtronic Business Restricted

This document is electronically controlled

CONFIDENTIAL 056-F275 Rev E Clinical Investigation Plan Template

Medtronic Expand URO Clinical Investigation Plan

MDT19051EINURO

Version 9.0

Page 75 of 111

Medtronic

Endpoint	Procedure Type	PG	Rationale

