7.9.3.1 Objectives, Endpoint Definitions and Derivations

Endpoint #	Objective	Endpoint Definition and Derivation
1	Overall Complication Rate	Rate of overall complications within 30 days is calculated as the proportion of subjects who experience any related (device, procedure, or underlying condition/disease) adverse event prior to or during the 30 calendar-days post-procedure. The AE start date collected with the adverse event will be used to determine whether a complication was experienced.
2	Operative Time	Operative time is defined as the difference in time in minutes between the procedure end time and the procedure start time. The procedure start time is the time of first incision and the end time is the time of skin closure.
3	Intraoperative Estimated Blood Loss	The estimated amount of blood loss is reported during the procedure in mL.
4	Transfusion Rate	Occurrence of a blood transfusion is captured as an adverse event. A blood transfusion is defined as an AE that resulted in any treatment and then a bleeding complication led to a blood transfusion and started prior to or during the 30 calendar-days post-procedure.
5	Device-related Conversion	A conversion is defined the same way as in Section 7.9.1.2 . A device related conversion is defined as a conversion where either the primary or any other reason for conversion is denoted as Adverse Event that is related to the device or procedure, Device Deficiency, Non-Subject Adverse Event, or Poor Visualization.

6	Hospital Length of Stay	
The length of hospital stay is the number of days that the subject was in the hospital from the start of the surgical procedure to hospital discharge. The number of days in the hospital can be found as the difference in minutes between the discharge date and time and the procedure date and time divided by 1440 min/hour, i.e.,
 $(Discharge Date and time - procedure date and time)/1440.$
7	Readmission Rate	A readmission in a subject is identified if a related (device, procedure, or underlying condition/disease) adverse event with a start date of or after the index procedure date and prior to or during the 30-calendar days post-procedure that resulted in the subject being hospitalized. Additionally, the hospital start date reported within the AE must be prior to or during the 30 calendar-days post-procedure and on or after the reported index procedure discharge date.

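### SAP endpoint 5 labels a conversion device-related for a procedure-only adverse event or for poor visualization of any cause, and no planned table gives a device-only rate.

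*SAP*

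**What the plan says.** The protocol lists the rate of device-related conversion as a secondary endpoint (5.1.4, 14.5) but does not define it. The definition is in SAP 7.9.3.1, endpoint 5. A conversion qualifies on its main reason or on a secondary one. The test reads: "reason for conversion is denoted as Adverse Event that is related to the device or procedure, Device Deficiency, Non-Subject Adverse Event, or Poor Visualization".

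Protocol Table 7 (12.4) gives two separate relatedness categories. The first reads "Device-related: An AE that results from the presence or performance (intended or otherwise) of the device"; the second, for procedure relatedness, reads "An AE that occurs due to any procedure related to the Hugo™ RAS System". Table 8 (12.5.1) has the investigator and the sponsor each classify relatedness to procedure, underlying condition and device.

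On purpose, Protocol 10.5 states: "The secondary endpoints of this study (operative time, device-related conversions, device deficiencies) will assess the overall performance" of the system. The Protocol 14.5 table adds "Device related conversions are expected to be a fraction of the total conversions" and sets a goal of 15% for each surgery type.

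SAP 7.9.3.5 reports the endpoint by surgery as a count and proportion with a 95% confidence interval. SAP 7.9.3.2 rules out hypothesis tests for secondary endpoints.

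**The concern.** A reader who sees a device-related conversion rate will take it as the share of operations abandoned for a reason attributed to the robot. The rule is wider than that in three ways:

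- An adverse event related to the procedure but not to the device is enough.
- Poor visualization is enough, with no requirement that the system caused it.
- Either may be a secondary reason.

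The study already collects the distinction that the rule merges. At stake is whether this descriptive rate can be read as evidence on device performance. No hypothesis, alpha level or sample size depends on it.

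**Working it through.** **1. The plan's own figure.** The 15% goal is 1 − 0.85 = 0.15, the complement of the 85% surgical-success goal. It reproduces. It is a goal for all conversions, carried over to the device-related subset.

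**2. Does each route require attribution to the device?**

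| Route in SAP endpoint 5 | Device attribution required? | Basis |
|---|---|---|
| AE related to the device | Yes | Protocol Table 7 |
| AE related to the procedure only | No | separate category in Tables 7 and 8 |
| Device deficiency | Yes, by definition | Protocol Table 7 |
| Non-subject AE | Yes, by definition: limited to events from use of the investigational device or comparator | Protocol Table 7, AE definition, Note 3 |
| Poor visualization | No | no qualifier in the SAP |

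The rule excludes a conversion whose only reason is an AE related solely to the underlying condition, or a reason not on the list.

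**3. Can the device-only rate be recovered elsewhere?**

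- SAP 7.9.1.7.3 tabulates conversions by type (open, laparoscopic, other robot), not by reason.
- SAP 7.9.2.7 and 7.9.3.5 plan device-only, procedure-only and condition-only analyses, but for major and overall complications. Endpoint 5 gets none.
- SAP endpoint 10 counts subjects with a device deficiency, whether or not they were converted.
- SAP 7.10 summarizes AE relatedness without linking it to conversion.

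None of these crosses conversion with its reason.

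**4. Size per case.** Cohorts are up to 55, 55 and 31 (Protocol 14.7). One conversion counted only through a route without device attribution adds:

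- 1/55 = 1.8 percentage points (nephrectomy or prostatectomy)
- 1/31 = 3.2 percentage points (cystectomy)

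**5. How many conversions to expect.** The documents give no distribution of conversion reasons, so a corrected device-only rate cannot be computed. For scale only, assume the literature mean for conversions of any cause, 0.022 (Protocol 14.4.1) or 0.024 (SAP 7.9.1.4), applies to every cohort:

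| n | n × 0.022 | n × 0.024 |
|---|---|---|
| 55 | 1.2 | 1.3 |
| 31 | 0.7 | 0.7 |
| 141 | 3.1 | 3.4 |

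On that assumption, a single case without device attribution could be most or all of a cohort's numerator.

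**6. Effect of one case on the reported result** (Clopper-Pearson 95% intervals):

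| n | 0 cases | 1 case |
|---|---|---|
| 55 | 0% (0 to 6.5%) | 1.8% (0.0 to 9.7%) |
| 31 | 0% (0 to 11.2%) | 3.2% (0.1 to 16.7%) |

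In cystectomy, one case takes the upper limit from below to above 15%. The plan does not judge the endpoint by its interval, so this shows sensitivity and is not a change of result.

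**The case against.** The case for leaving the rule alone has five parts.

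- **No competing definition.** The protocol names the endpoint without defining it, so the SAP breaks no protocol rule. Protocol 14.5 and SAP 7.9.3 also describe the secondary endpoints as exploring outcomes linked to the procedure or the disease. This stands: the difficulty lies in the label, the use stated in Protocol 10.5 and the separate relatedness categories.
- **Procedure relatedness is tied to the robot.** The Table 7 sentence ends with the Hugo system, and in a robotic operation device and technique may be hard to separate. An inclusive numerator is defensible. Procedure relatedness nevertheless remains a separate category, rated separately.
- **The AE route is needed.** Protocol 12.2 sends a deficiency that causes a subject AE to the AE form only. This is correct, and it supports keeping device-related AEs. It does not require procedure-only AEs.
- **Visualization is a system function.** The 3D display is in the console and the endoscope system is in the tower (Protocol 7.1.1, 7.1.3). Some poor visualization will be the system's doing, so dropping this route would undercount. Requiring a recorded deficiency alone would also undercount, because of the 12.2 rule. Neither point justifies counting it whatever the cause.
- **The rule is conservative and untested.** It can only raise the rate attributed to the device, and study success does not depend on it. This stands and limits the weight of the point.

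A reader might go further and infer that the rate as derived comes close to the total conversion rate. The documents do not support that: they give no distribution of reasons, the full list of reasons is not shown, and the rule does exclude some. The protocol's expectation of a fraction of all conversions is not contradicted.

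**Conclusion.** The point holds and is minor. Followed as written, SAP endpoint 5 can report conversions with no device attribution as device-related, and nothing planned lets a reader take them out. The overstatement can be anything from nil to the whole counted numerator. Each case is worth about 1.8 points in a cohort of 55 and 3.2 points in a cohort of 31, assuming the cohorts reach their maximum sizes and all subjects have data. The statement that one case could dominate a numerator rests on the further assumption that conversion is about as rare as in the literature.

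A reader might also infer that the definition flatters the device or threatens the primary effectiveness result. Neither follows: the error runs against the device, and the primary endpoint counts every conversion whatever its reason.

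**What to change.** Amend SAP 7.9.3.1 and 7.9.3.5 in three steps:

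1. Keep the present rule, but label it *device- or procedure-related conversion*.
2. Beside it, by surgery type, report a device-only rate. Count a conversion whose primary or other reason is a device-related AE (any device rating other than Not Related, as the SAP already does in its exploratory complication analyses), a device deficiency, a non-subject AE, or poor visualization attributed to the system by a recorded deficiency or a device-related AE. Non-subject AEs need no further restriction, because Table 7 already supplies it.
3. Tabulate all conversions by primary and other reasons.

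The cost is SAP wording, one extra row and one extra table. Conversion reason, AE relatedness and device deficiency are already collected. The drawback is that the device-only rate is less conservative and would be set against a 15% benchmark carried over from all conversions, which a narrower numerator meets more easily. Both rows should therefore always be shown together.

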5.1.4 Secondary Endpoints

Secondary objectives include descriptive analyses of secondary endpoints.

The following safety and performance data shall be collected through 30 days post-procedure to assess the overall safety and performance of the Medtronic Hugo™ RAS System when used for urologic RAS:

- Complication rate: Overall rate of subjects with one or more complications (Clavien-Dindo Grade I or higher), from the first incision through 30 days post-procedure
- Operative time
- Intraoperative estimated blood loss (mL)
- Transfusion rate
- Rate of device-related conversion
- Hospital length of stay
- Readmission rate (through 30 days)
- Reoperation rate (through 30 days)
- Mortality rate (through 30 days)
- Rate of device deficiencies

The following long-term secondary endpoints will be assessed through 5 years in oncologic subjects:

- Overall survival
- Progression-free survival
- Disease-free survival

Performance Goals for Secondary Endpoints

The details are summarized in the table found in **Section 14.5**.

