10.6 Assessment of Safety

Safety will be evaluated through the study primary endpoint (major complications) and several secondary endpoints (**Section 5.1.4**).

Safety will also be assessed by monitoring the occurrence of adverse events (AEs), serious adverse events (SAEs), deaths, adverse device effects (ADE), serious adverse device effects (SADE), unanticipated adverse device effects (UADE) or device deficiencies. Adverse event assessments will take place starting with the point of consent, through the end of study exit through 5-year follow-up, or until resolution whichever comes first and will be recorded in the eCRF.

Medtronic Business Restricted

This document is electronically controlled

CONFIDENTIAL 056-F275 Rev E Clinical Investigation Plan Template

AEs will be collected from the time of consent. AEs occurring in subjects excluded from the full analysis set (FAS) (**Section 14.1**) will be followed post-consent through study exit and will be reported in a listing in the clinical study report (CSR).

These AEs will not be included in the FAS summary analysis for either AE reporting or the analysis of the primary and secondary endpoints.

For the FAS, the type, incidence, severity, duration, and procedure/device relatedness of AEs will be reported. AEs for all FAS subjects will be analyzed from first incision through the study exit.

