10.9.2 Study Completed

At the completion of the 30 (+7) day follow-up visit, non-oncologic subjects will be exited from the study. At the completion of the 5-year follow-up visit, oncologic subjects will be exited from the study. The 30 (+7) day or the 5-year follow-up visit and exit visit should be combined, and either the 30 (+7) or the 5-year follow-up eCRF and the Study Exit eCRF need to be completed.

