4.3 Ancillary Objectives

Descriptive analyses of other pre-specified outcome measures beyond the primary and secondary objectives will be exploratory in nature and are not intended as a focus of the study for the evaluation of the study device.

The following data will be collected as applicable:

- Rate of negative surgical margins
- Lymph node yield
- Warm ischemia time
- Surgeon experience

5. Investigation Plan

This is a prospective, multicenter, single-arm pivotal study to be performed in up to 141 subjects undergoing a urologic RAS procedure using the Medtronic Hugo™ RAS System. Subjects without an oncologic indication will be followed for 30 days (+7 days) post procedure. Oncologic subjects will be followed through 5 years. This study will be conducted using up to six investigative sites in the United States of America (USA).

This study will have two phases, a roll-in phase and open enrollment phase. Two (2) sites will consecutively enroll a total of 15 subjects who will be treated with the Hugo™ RAS System as “roll-in cases”. These subjects will undergo the same preoperative and postoperative assessments (with the same schedule) as patients who are enrolled in the open enrollment phase. Outcomes through 30 days for the first 15 roll-

in cases will be provided in a summarizing fashion and provided to the FDA for initial review without statistical inferences. The roll-in subjects will be included in the primary analysis with the open enrollment subjects and for all required reports.

Following completion of the roll-in phase and sponsor approval, all sites will be allowed to enroll patients in the study. During the open enrollment phase, all patients enrolled will follow the Clinical Investigation Plan.

The expected study duration is approximately 5 years. The duration of individual subject participation will be approximately 67 days (-30 to 30+7) for non-oncologic subjects and 5 years for oncological subjects.

6. Determination of Sample Size

The sample size for the study was estimated based on the primary safety and effectiveness hypotheses.

Power calculations were performed using statistical software NCSS PASS 2023.

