8	Reoperation Rate	Reoperation through 30 days is identified in a subject if they experience a related (device, procedure, or underlying condition/disease) adverse event that resulted in treatment with a surgical procedure and the AE start date was prior to or during the 30-calendar days post-procedure.
9	Mortality Rate	Death through 30 days is identified as an AE that led to death which occurs during the procedure or up to the 30 calendar-days post-procedure.
10	Device Deficiencies	A subject is identified as experiencing a device deficiency if a device deficiency occurred before, during, or after the subject's procedure.
11	Overall Survival	Subject death will be identified as an adverse event that leads to death where the adverse event start date is on or after the procedure date or if the subject is noted by the site to have died during follow-up. Time to death will be calculated as the difference in days between death and the procedure date.
12	Progression-free Survival	Disease progression will be identified in a subject if their disease state is noted by the site, during follow-up, as "disease reoccurrence, disease progression", or if subject death had been noted. This is assessed as either at the time of the follow-up visit or at the time of last contact, whichever is earlier will be denoted as the time of disease

		progression. Time to disease progression is calculated as the difference in days between disease regression and the procedure date.
13	Disease-free Survival	Disease reoccurrence will be identified in a subject if the subject disease state is noted by the site, during follow-up, as “disease reoccurrence, disease progression”, “disease reoccurrence, disease stable”, or if subject death had been noted. This is assessed either at the time of a follow-up visit or at the time of last contact, whichever is earlier will be denoted as the time of disease reoccurrence. Time to disease reoccurrence will be calculated as the difference in days between disease reoccurrence date and the procedure date.

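### SAP endpoint 8 dates 30-day reoperation by the start of the adverse event and not by the operation, so an operation after day 30 can count as a 30-day reoperation

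*SAP*

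**What the plan says.** The protocol lists the reoperation rate among the short-term secondary endpoints (Section 5.1.4), labels it as running through 30 days, and gives no derivation. The derivation is in SAP 7.9.3.1, endpoint 8: "Reoperation through 30 days is identified in a subject if they experience a related" (to device, procedure, or underlying condition or disease) "adverse event that resulted in treatment with a surgical procedure and the AE start date was prior to or during the 30-calendar days post-procedure". The only date in the rule is the start of the adverse event (AE).

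Endpoint 7, readmission, is built differently. The AE must start on or after the index procedure date and by day 30. In addition, "the hospital start date reported within the AE must be prior to or during the 30 calendar-days post-procedure and on or after the reported" index discharge date. The readmission is therefore dated by the hospitalization as well as by the AE.

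Three other provisions bear on the reading:

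- Protocol 10.6: "AEs for all FAS subjects will be analyzed from first incision through the study exit". Intraoperative events are in scope.
- SAP Section 5: "Oncologic subjects will be followed through 5 years". Protocol Table 6 has AEs followed until they resolve or the subject exits, and it collects reoperation at discharge, at the 30-day visit and at the Year 1 to 5 contacts.
- Protocol 10.9.2: "At the completion of the 30 (+7) day follow-up visit, non-oncologic subjects will be exited from the study".

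**The concern.** The endpoint's name promises operations done within 30 days. The rule delivers operations done at any time for events that began within 30 days. For a complication managed conservatively at first and operated on later, the two differ.

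The rule also does not say that the operation must be a second one. An injury made and repaired during the index surgery is an AE starting on day 0, and nothing in endpoint 8 excludes it if its treatment is recorded as surgical.

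The result is set beside a performance goal that Protocol 14.5 derives from a literature rate of reoperation within 30 days. If the numerator follows a different definition, the comparison is not like with like. The rate also comes to depend partly on how long each subject has been followed when the data are cut.

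**Working it through.** **The benchmark.** Protocol 14.5, prostatectomy row: highest literature-reported 30-day reoperation rate 0.156, plus an absolute margin of 0.10. 0.156 + 0.10 = 0.256, which reproduces the stated 25.6%. The nephrectomy and cystectomy goals are taken over from prostatectomy because no literature was found for them.

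**The two rules side by side.**

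| Condition | Endpoint 7, readmission | Endpoint 8, reoperation |
|---|---|---|
| AE related | yes | yes |
| AE start by day 30 | yes | yes |
| AE start on or after index procedure | yes | not stated (Protocol 10.6 supplies first incision) |
| Date of the event itself by day 30 | yes, hospital start date | not stated |
| Event separate from the index episode | yes, on or after index discharge | not stated |

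**Hypothetical cases against endpoint 8, read literally.**

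1. Oncologic subject, related leak starting on day 25, operated on in month 6. Related: yes. Surgical treatment: yes. AE start by day 30: yes. Counted, although the operation was not within 30 days.
2. Vessel injury at the index surgery, repaired in the same session. AE start by day 30: yes, day 0. Surgical treatment: depends on how the AE form records the repair. Counted if recorded as surgical treatment.
3. Related leak starting on day 10, operated on on day 12. Counted, correctly.

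The rule does not lose true cases among operations for a related AE: if the operation took place by day 30, the AE that led to it also started by day 30. The error therefore goes one way, upward.

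**Size per subject.** The planned maxima are 55 nephrectomy, 55 prostatectomy and 31 cystectomy (Protocol 14.7).

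- 1/55 = 1.8 points
- 1/31 = 3.2 points

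**Illustration, under assumptions.** Take a true rate of 6.2%, the prostatectomy literature mean, for every cohort. That gives 0.062 × 55 = 3.4, about 3 subjects, and 0.062 × 31 = 1.9, about 2 subjects. Let 0 to 3 subjects be wrongly counted. The intervals are Clopper-Pearson 95%; the SAP names no interval method for this endpoint.

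| Wrongly counted | n=55 | n=31 |
|---|---|---|
| 0 | 3/55 = 5.5% (1.1 to 15.1) | 2/31 = 6.5% (0.8 to 21.4) |
| 1 | 4/55 = 7.3% (2.0 to 17.6) | 3/31 = 9.7% (2.0 to 25.8) |
| 2 | 5/55 = 9.1% (3.0 to 20.0) | 4/31 = 12.9% (3.6 to 29.8) |
| 3 | 6/55 = 10.9% (4.1 to 22.2) | 5/31 = 16.1% (5.5 to 33.7) |

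The point estimate passes 25.6% only at 15/55 (27.3%) or 8/31 (25.8%). From these starting counts, that takes 12 or 6 wrongly counted subjects. The upper confidence limit is more sensitive: in cystectomy, one extra subject moves it from 21.4% to 25.8%.

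**The case against.** **AE onset is the SAP's general convention.** The primary safety endpoint and several secondary endpoints are dated by AE start within 30 calendar days, and the SAP's version history says that the 30-day secondary definitions were aligned with primary safety. Attributing an operation to a complication that began in the window is a coherent choice. This stands as an explanation of the wording. It does not make a month-6 operation a 30-day reoperation, and endpoint 7 shows that the SAP departs from the convention where the event has its own date.

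**The error is conservative.** It raises a safety rate and cannot flatter the device. This is correct and limits the weight of the point. The rate is still not the one named, nor the one behind the benchmark.

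**The endpoint is descriptive.** SAP 7.9.3.2 excludes hypothesis testing, and SAP 7.9.3 and Protocol 14.5 make the goals benchmarks for interpretation. This stands in full.

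A reader might also draw stronger conclusions that the documents do not support:

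- *That index-session repairs are certain to be counted.* This turns on the AE form, which is not in the documents. A programmer may also read a second operation into the word reoperation.
- *That non-oncologic subjects with late surgery are never counted.* Exit at 30 (+7) days is the norm, but Protocol 10.9.1 recommends following ongoing system- or procedure-related AEs until they resolve, or until no further action is planned, before exit.
- *That the rate will rise between the 30-day report and the final report.* Protocol 14.2 puts the 30-day analyses after all subjects complete 30-day follow-up and the 5-year secondary analyses in the final report. Protocol 16.9.3 says that the final report covers all objectives, but nothing expressly schedules a re-run of the 30-day rate. Subjects enrolled early may, however, have more than 30 days of follow-up at the first analysis.

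**Conclusion.** The point holds as a defect in a stated rule. Endpoint 8 does not limit the date of the operation and does not require an operation separate from the index procedure, so its literal result is not a 30-day reoperation rate. The late-operation half follows directly from the text and concerns mainly oncologic subjects. The index-session half is conditional on the AE form.

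The documented size is 1.8 points per affected subject at n=55 and 3.2 points at n=31, always upward. How many subjects would be affected is unknown. The illustrated rates rest on an assumed 0 to 3 errors and on a 6.2% mean from two prostatectomy cohorts (95% CI 0.005 to 0.469), with no literature basis for nephrectomy or cystectomy. They should not be read as forecasts.

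A reader might infer that the study's conclusions are at risk. They are not: no primary test, alpha level, sample size or success criterion depends on this endpoint. It should be corrected because the wording departs from the endpoint's name and benchmark and the correction costs very little.

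**What to change.** In SAP 7.9.3.1, endpoint 8, add two conditions in the manner of endpoint 7:

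1. The surgical procedure is a separate operation performed after the end of the index procedure (skin closure).
2. The date of that operation falls within 30 calendar days post-procedure.

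Use the treatment or reoperation date that is collected. Table 6 has a Reoperation row, but the documents do not show which date fields stand behind it. If no operation date is on the form, add one field. Report surgical repairs made during the index session separately, as intraoperative events.

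The cost is a short SAP amendment and a date condition in the program, plus one form field at most. It needs no extra visits or subjects and leaves the 25.6% benchmark unchanged.
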